7.4 Procedures for Recording and Reporting of Adverse Events

Event	Reporting Procedures
	notifying Regulatory Authorities of any other serious unexpected suspected adverse reaction as soon as possible but in no case later than 15 calendar days after the Sponsor's initial receipt of the information.
	Sponsor Contact Information for SAE Reporting
	Email: eFax number:

7.5 Reporting of Pregnancy

Although not an AE in and of itself, pregnancy as well as its outcome must be documented via the *Pregnancy Report Form provided by the Sponsor*. Any pregnancy occurring in a participant or participant's partner from the time of consent to 30 days after the last dose of IP must be reported and then followed for outcome. Newborn infants born to the subject or subject's partner should be followed until 30 days old.

A FCBP must discontinue SL-172154 immediately if they become pregnant during the study. To ensure subject safety, each pregnancy must be reported to the Sponsor within two weeks of learning of its occurrence. The pregnancy must be followed to determine outcome (including premature termination) and status of mother and child. Pregnancy complications and elective terminations for medical reasons must be reported as a SAE. Spontaneous abortions must be reported as a SAE.

Any SAE occurring in association with a pregnancy brought to the investigator's attention after the subject has discontinued SL-172154 must be promptly reported to the Sponsor.

7.6 Reporting of Overdose

The following events should also be reported to the Sponsor *within 24 hours* of knowledge of the event:

- An overdose of SL-172154
- Suspected transmission of an infectious agent due to contamination of drug product
- Other events related to misuse of IP

7.7 Study Halting Rules

Administration of IP will be halted if a fatal SAE is reported to the Sponsor related to SL-172154 monotherapy or combination therapy. The Sponsor will inform the investigators immediately if such an event is reported and screening and enrollment will stop accepting new study subjects. The Sponsor will convene an ad hoc meeting of the SMC to review the SAE and overall safety profile and provide recommendations. The study Sponsor will inform the regulatory authorities (i.e., FDA, European Medicines Agency, etc.) of the temporary halt and the disposition of the study.

7.8 Safety Oversight

An SMC will be implemented in this study and will consist of investigators and Sponsor representatives. SMC meetings will be conducted monthly (or more frequently if required) during dose escalation provided subjects have been enrolled and data are available to be reviewed. The SMC will operate in accordance with the SMC charter which will define roles and accountabilities and the process for safety review. Throughout the conduct of the study, safety data will be reviewed for each subject on an ongoing basis. Based on the AE profile, severity of the DLTs, indicators of potential anti-tumor activity, and other factors, a recommendation on whether to modify the dose and/or study design; or continue enrollment will be made by the Sponsor collaboratively with input from the SMC. Regulatory authorities and IRBs/IECs will be notified of any decisions to prematurely halt the study or subject enrollment. (See section 14.1 for details on safety meetings).

8. ANTI-TUMOR ACTIVITY ASSESSMENTS

Although the clinical benefit of SL-172154 has not yet been established, the intent of offering this IP is to provide a possible therapeutic benefit, and thus the participant will be carefully monitored for tumor response and symptom relief in addition to safety and tolerability. For the purposes of this study, participants should be evaluated for response as outlined in the SOA. Confirmatory scans should be performed at least 4 weeks (>28 days) after initial documentation of an objective response or progressive disease. All participants who underwent the first post baseline disease assessment at the 8-week time point or progress or die before to the first post baseline disease assessment will be considered evaluable for response.

Assessments must be performed on a calendar schedule and should not be affected by dose interruptions or delays. Refer to the SOA (Section 6) for the schedule of disease assessments. More frequent disease assessments may be performed at the discretion of the investigator. For subjects whose disease may be followed by well-characterized tumor markers (i.e., CA-125), disease assessments should include results of tumor marker assessments. If study treatment is withdrawn for reasons other than disease progression, radiographic disease assessments should continue as per the SOA until documented disease progression, the start of new anti-cancer therapy, withdrawal of consent or death. See Sections 8.2 for criteria for continuing treatment past disease progression.

8.1 Disease Assessment

Imaging studies, preferable by contrasted computed tomography scan for disease assessment of chest, abdomen and pelvis and all other sites of known disease will be performed at baseline and at the following intervals until disease progression: every 8 weeks until week 24 and every 12 weeks thereafter until year 2 and every 6 months until study conclusion. PET-CT, MRI, and/or bone scan should be performed as clinically indicated. The same imaging modality used at baseline should be employed subsequently. Confirmatory scans should be performed at least 4 weeks (>28 days) after initial documentation of an objective response or progressive disease. Contrast enhanced imaging is required unless the subject is precluded from receiving contrast (e.g., hypersensitivity, renal impairment).

Treatment beyond progression will be permitted provided the subject meets protocol specified criteria in Section 8.2. If subjects discontinue investigational therapy prior to progressive disease,

they should continue to be followed with radiologic assessments until disease progression, start of a new anti-cancer therapy, withdrawal of consent or death.

8.1.1 Assessment of Response

Investigator-assessed response and progression will be evaluated in this study using RECIST v1.1 [Eisenhauer, 2009] and iRECIST [Seymour, 2017]. The RECIST v1.1 guideline and iRECIST guideline are included in this document (Section 16.5).

8.2 Criteria for Treatment Beyond Initial Progression

Subjects will be permitted to continue IP beyond initial progressive disease provided the subject does not have clinical symptoms of progression, is tolerating IP, has experienced no decline in their ECOG performance status and is gaining clinical benefit as assessed by the investigator. The subject must be made aware of the potential benefits and risks of continuing the IP in the setting of progressive disease by signing a separate written informed consent.

The subject may continue to be treated until one of the following criteria is met:

- Meets any of the criteria for discontinuation of IP (see Section 3.7)
- Develops clinical symptoms or signs such that the benefit-risk ratio of continuing therapy is no longer justified
- Experiences rapid progressive disease with risk to vital organs or critical anatomical sites requiring urgent medical intervention

9. DATA ANALYSIS AND STATISTICAL CONSIDERATIONS

9.1 Study Design and Sample Size Determinations

The dose escalation will utilize a mTPI-2 design [Guo, 2017] with target DLT rate of 30% for the MTD. The DLT evaluable population is defined in section 9.2.1.

The mTPI-2 design employs a simple Beta-Binomial Bayesian model with decision rules based on the unit probability mass from the posterior probability of DLT rate. With the target DLT rate of 30%, the posterior probability of DLT rate unit interval (0, 1) is divided into subintervals with equal length of 0.1 that correspond to different dose escalation decisions: subinterval of (0.25, 0.35) is to stay at the current dose, subintervals below 0.25 is to escalate to next higher dose, and subintervals above 0.35 is to de-escalate to the next lower dose. Subjects will be enrolled in cohorts of approximately 3 subjects during the dose escalation. After each cohort of approximately 3 subjects, the posterior unit probability for subintervals will be calculated based on a noninformative prior distribution for the DLT rate (Beta (1,1)) and the total number of subjects with DLTs and DLT evaluable subjects for the current dose. A dose escalation/stay/de-escalation decision that corresponds to the subinterval with the highest unit probability mass will be selected. A minimum of 3 DLT evaluable subjects will be enrolled to a dose level and evaluated for DLT before a dose escalation/stay/de-escalation decision can be made unless unacceptable toxicity is observed prior to the enrollment of 3 subjects e.g., two subjects experience DLT before the third subject enrolls. A dose level will be considered unsafe, with unacceptable toxicity and no additional subjects enrolled at that dose level and above, if it has an estimated 95% or more probability of exceeding the target DLT rate of 30%. The maximum number of subjects evaluated for DLT for each dose level will be 12 subjects (about 4 cohorts of 3 subjects) if the dose escalation

decision is to stay at the current dose from the first 3 cohorts. Based on the above design, the dose escalation decision rules are as the following for each dose level:

- When the number of DLT evaluable subject is <12 subjects:
 - Dose escalate if the observed DLT rate <25%;
 - Stay at the current dose if the observed DLT rate between 25%-33%;
 - Dose de-escalate if the observed DLT rate >33%;
- After reaching the maximum 12 subjects, the dose escalation decision will be either escalate or de-escalate as the following:
 - Dose escalate if the observed DLT rate $\leq 25\%$;
 - Dose de-escalate if the observed DLT rate \geq 33%;

See Table 7 for dose escalation decision rules based on the total number of subjects evaluable for DLT and the number of DLTs observed.

Number	Number of Subjects										
of subjects with DLTs	3	4	5	6	7	8	9	10	11	12	
0	E	E	Е	E	E	Е	Е	E	E	E	
1	S	S	Е	E	Е	Е	Е	E	Е	E	
2	D	D	D	S	S	S	Е	E	E	E	
3	DU	DU	D	D	D	D	S	S	S	Е	
4		DU	DU	DU	D	D	D	D	D	D	
5			DU	DU	DU	DU	DU	D	D	D	
6				DU	DU	DU	DU	DU	DU	D	
7	•		•		DU	DU	DU	DU	DU	DU	
8	•					DU	DU	DU	DU	DU	
E = eso	E = escalate to the next higher dose level				S = stay at the current dose level						
$\mathbf{D} = \mathbf{d}\mathbf{e}$	D = de-escalate to the next lower dose level			DU = de-escalate to the next lower dose level and current dose level will never be used again due to unacceptable toxicity							

Table 7. Dose Escalation Decision Rules for Each Dose Level based on mTPI-2

Note: For each dose level, a minimum of 3 subjects will be enrolled and evaluated before a dose escalation/stay/deescalation decision can be made unless unacceptable toxicity is observed prior to the enrollment of 3 subjects e.g., 2 subjects experience DLT before the third subject enrolls.

Sample Size Determination:

The planned sample size is approximately 33-54 subjects. If only Schedule 1 is evaluated, the planned total sample size is 21 for dose escalation. If Schedule 1 and Schedule 2 are both fully evaluated in dose escalation, the maximum planned sample size for dose escalation is 42. This sample size assumes evaluation of five dose levels with approximately 21 subjects treated in the

dose escalation cohorts for each schedule 1 and schedule 2, assessment of approximately 6 subjects in an optional pharmacodynamic cohort and assessment of approximately 6 subjects in dose expansion. Overall, approximately 6-12 subjects are to be treated at the RP2D for SL-172154. In dose escalation cohorts, subject may be replaced if not DLT evaluable.

NOTE: The planned sample sizes may be revised if additional dose levels are evaluated or if more subjects (i.e., 4 subjects dosed in a cohort to ensure that at least 3 subjects are DLT evaluable) are enrolled. The Sponsor, in consultation with the SMC, may also elect to add subjects to the dose escalation if additional data are needed for RP2D determination.

9.2 Statistical Analyses

Complete details of the statistical analysis will be provided in the Statistical Analysis Plan (SAP). Any deviations from, or additions to, the original analysis plan described in this protocol will be documented in the SAP and final study report.

9.2.1 Analysis Populations

Population	Description
Enrolled	All subjects who have signed the main study inform consent form (ICF).
Screen Failures	All subjects who have signed the main study ICF but have not received any study treatment.
All Treated	All subjects who have received at least one dose of IP. Safety data will be evaluated based on this population.
DLT Evaluable	All treated subjects 1) who have received ≥ 2 of the 3 scheduled doses of IP on schedule 1 or who have received ≥ 2 of the 4 scheduled doses of IP on schedule 2 during cycle 1 and complete the safety follow-up through the 28-day DLT evaluation period; or 2) who experience any DLT during the DLT evaluation period. DLT evaluable subjects will be used to guide dose escalation and to determine the MTD or MAD.
Response Evaluable	Subjects in the All Treated Population who have a baseline disease assessment and have at least one post-baseline disease assessment or have progressed or died before the first post-baseline disease assessment.
Pharmacokinetic	Subjects in All Treated Population from whom at least one PK sample is obtained and analyzed. The PK population will be used for the PK analysis.
Pharmacodynamic	Subjects in the All Treated Population for whom at least one pharmacodynamic sample is obtained and analyzed. The pharmacodynamic population will be used for the pharmacodynamic data analysis.

For the analysis, the following populations are defined:

9.2.2 Interim Analyses

During the dose escalation, the number of subjects with DLTs will be determined after each cohort of approximately 3 subjects has been evaluated for DLT. The summary of DLTs for each dose level will be based on the number of subjects with DLTs from all subjects dosed and evaluated at

CONFIDENTIAL Compound: SL-172154

the corresponding dose level who meet the definition of the DLT Evaluable Population. Selected AE summary tables and listings may be provided during dose escalation to support dose escalation decisions.

9.2.3 General Data Analysis Consideration

Tabular summaries will be presented by dose levels/schedule/cohorts and total number of subjects in the corresponding population. Categorical data will be summarized by the number and percentage of subjects in each category. Continuous variables will be summarized by descriptive statistics.

As it is anticipated that accrual will be spread thinly across centers and summaries of data by center would be unlikely to provide valuable information, data from all participating centers will be pooled prior to analysis.

All data up to the time of study completion/withdrawal from study will be included in the analysis for each subject, regardless of duration of treatment.

9.2.4 Safety Analyses

The safety evaluation will be based on the All Treated Population and the DLT evaluation will be based on the DLT evaluable population.

DLTs will be summarized by dose level. Frequency tables will be used to describe safety and tolerability parameters AEs, irAEs, SAEs, fatal SAEs and AEs leading to discontinuation of SL-172154. Graphs may also be presented where appropriate. AEs will be mapped to a Medical Dictionary for Regulatory Activities (MedDRA) preferred term and system organ classification. Laboratory abnormalities will be graded according to the NCI CTCTAE v5., if applicable. Concomitant medications will be coded using the World Health Organization Drug Dictionary.

MTD: The MTD will be estimated using isotonic regression (based on the DLTs observed in DLT evaluable subjects). Specifically, the MTD is the dose for which the isotonic estimate of the DLT rate is closest to the target DLT rate of 30%. If two or more doses tie for the smallest difference, perform the following rules:

- If the estimated DLT rate < 30% for all doses, then select the higher dose among the tied doses;
- If the estimated DLT rate for the tied doses are a combination of < 30% for and > 30%, then select the higher dose among the tied doses;
- If the estimated DLT rate > 30% for all dose, then select the lower dose among the tied doses

NOTE: For subjects who undergo intra-subject dose escalation, DLTs will only be assessed during the DLT period applicable on the subject's initial dose level.

A MAD will be reported if the observed DLT rate is <25% among all dose levels. Otherwise, an MTD will be reported.

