3. STUDY DESIGN

3.1 Description of Study Design

This clinical trial is a FIH, open label, multi-center, dose escalation Phase 1 study of SL-172154 (see SCHEMA).

This Phase 1 trial is designed to evaluate the safety, PK, pharmacodynamic effects, and anti-tumor activity of SL-172154 monotherapy. Subjects with platinum-ineligible ovarian, fallopian tube, and primary peritoneal cancers (Section 4.1) are eligible for treatment.

Dose Escalation

Dose escalation will utilize the modified Toxicity Probability Interval (mTPI-2) design [Guo, 2017] with target DLT rate of 30% for the MTD. The dose escalation decision rules are outlined in Table 7 in Section 9.1. Subjects will be enrolled in cohorts of approximately 3 subjects into sequential dose levels of SL-172154 and evaluated for DLT (see Section 3.4 for Definition of DLT) during the 28-day DLT evaluation period starting from the first dose of SL-172154. At each dose level, a minimum 3-day stagger between dosing the first and second subject is required. The planned dose escalation is in half-log increments as outlined in Table 1 and Section 3.3. During dose escalation, two possible schedules (Schedule 1 and Schedule 2) for administration of SL-172154 may be explored as outlined in Section 3.3. Schedule 1 will be evaluated first. A transition to Schedule 2 may be implemented for reasons outlined in Section 3.2.1. If Schedule 2 is opened for enrollment, then enrollment on Schedule 1 will be halted. If Schedule 2 is opened, the Sponsor may also elect to stop enrollment in Schedule 2 early (e.g., based on safety) and resume enrollment in Schedule 1. The MTD or MAD may be determined for either Schedule 1 or Schedule 2. Alternatively, a less intensive dosing schedule may be instituted if safety, pharmacokinetic and/or pharmacodynamic data on Schedule 1 support less frequent dosing of SL-172154.

CONFIDENTIAL Compound: SL-172154

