Evaluation of an Alternative Dosing Schedule: Safety, pharmacokinetic and/or pharmacodynamic data from the dose escalation cohorts and pharmacodynamic cohorts, if available, may support exploration of a more or less intensive dosing schedule for SL-172154. If these data from Schedule 1 support exploration of more frequent dosing (see Section 3.2.1 for criteria needed to transition to Schedule 2), then cohort enrollment on Schedule 2 will be instituted in lieu of Schedule 1. The starting dose on Schedule 2 will be at a dose level that has completed evaluation for safety on Schedule 1 as defined by the mTPI-2 design. Dose escalation (or de-escalation) may then proceed on schedule 2 as shown in Table 1. During dosing on Schedule 2, SL-172154 will be administered once weekly (D1, D8, D15, and D22) every 28 days. If less frequent dosing is supported by safety, pharmacokinetic and/or pharmacodynamic data, SL-172154 may be administered once every two weeks, once every three weeks or once every four weeks. The starting dose on a less frequent schedule would be instituted at a dose level that has completed evaluation for safety as defined by the mTPI-2 design, emerging safety data and as recommended by the SMC.

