Schedule 1 will be evaluated first. A transition to Schedule 2 may be implemented if pharmacodynamic effects are not present or detectable in Schedule 1, or pharmacokinetic parameters from Schedule 1 may suggest that a more frequent dosing schedule is warranted. If Schedule 2 is opened for enrollment, the enrollment on Schedule 1 will be paused. Schedule 2 may stop enrollment earlier (e.g., based on safety) and enrollment in Schedule 1 may be resumed. The

MTD or MAD may be determined for either Schedule 1 or Schedule 2. Alternatively, a less intensive dosing schedule may be instituted if safety, pharmacokinetic and/or pharmacodynamic

The planned dose escalation is in half-log increments as outlined in Table 1.

Table 1: SL-172154 Dose Escalation Plan in Phase 1

data on Schedule 1 support less frequent dosing of SL-172154.

Dose Level	IV Dose of SL-172154 (mg/kg) ^{a,b,c,d}	Duration of Infusion ^e
Level 1 - starting dose	0.1	30 minutes (+/- 10 minutes)
Level 2	0.3	30 minutes (+/- 10 minutes)
Level 3	1.0	30 minutes (+/- 10 minutes)
Level 4	3.0	60 minutes (+/- 15 minutes)
Level 5	10.0	60 minutes (+/- 15 minutes)

- a) Dosing will begin on Schedule 1 with SL-172154 administered in 28-day cycles on days 1, 8, and 15 in cycle 1 and then on days 1 and 15 in cycles \geq 2.
- **b)** Dose escalation on Schedule 2 may be tested. If Schedule 2 is opened, SL-172154 may be administered once weekly on days 1, 8, 15 and 22 of each 28-day cycle.
- c) Intermediate or higher dose levels may be tested based on emerging safety and pharmacodynamic data.
- d) The actual body weight in kilograms (kg) will be used for dose calculation in all subjects whose body weight is ≤100 kg. For subjects with body weight >100 kg, the dose to be administered should be the same as that calculated for a subject weighing 100 kg.
- e) Infusion time may change based on final drug volume needed for administration, safety and tolerability of the infusion for the subject and/or observed safety findings during the study. Protocol Clarification Memo dated on 04MAR2022 clarified that the duration of infusion was to be increased from 60 minutes to 120 minutes (± 20 minutes) for 10 mg/kg dose level. Protocol Clarification Memo dated on 3JUN2022 clarified that the duration of infusion was to be increased from 60 minutes to 120 minutes (± 15 minutes) for 3 mg/kg dose level.

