5.3.1 Premature Withdrawal and Missing Data

Subjects who prematurely withdraw from the study will be included in analyses up to the time of withdrawal, regardless of the duration of treatment and survival follow-up.

Missing data occurs when any requested data is not provided, leading to blank field on the collection instrument. Answers such as "Not applicable", "Not evaluable", etc. are not considered to be missing data and should be displayed as such.

For the time to event endpoints including DOR, PFS and OS, the missing data handling method will be censoring. Censoring mechanisms for these endpoints are described in Section 7.

The length of study treatment for each subject will depend on the safety, tolerability and efficacy of the treatment, so the duration of treatment will vary across subjects. Similarly, the duration of follow up for survival will also vary. All time to event endpoints will be analyzed using suitable statistical methods.

In the event that the study is prematurely discontinued, the study team will review the data to assess which statistical analyses are still considered appropriate.

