8.1 Maximum Tolerated Dose Evaluation

The MTD evaluation will be based on the DLT Evaluable Population. The number and percentage of subjects with DLT will be presented by dose schedule and level for dose escalation cohorts. The MTD level will be indicated in the summary.

The MTD will be estimated using isotonic regression (based on the DLTs observed in the DLT evaluable subjects). A MAD will be reported if the DLT rate never reaches $\geq 25\%$. Otherwise, an MTD will be reported. Isotonic regression is a way to estimate the MTD under the assumption that toxicity increases with dose. When using isotonic regression, the first step is to identify the doses where the dose-toxicity monotonicity assumption is violated. The DLT estimate is then adjusted for the violators such that the final estimate of the DLT rate increases with the dose. The target DLT rate is then used to select the MTD. For example, suppose that when the trial is completed, the observed DLT rates [# subjects who experienced DLT]/[# evaluable subjects] at five dose levels are (0/3, 1/3, 0/3, 4/15, 2/4). In this example the observed DLT rate at Dose Level 2 (i.e., 1/3=33%) is higher than the observed DLT rate at Dose Level 3 (i.e., 0/3=0%). To adjust for this violation, the DLT estimates are replaced with their average, i.e., (1/3+0/3)/2=1/6, resulting in the isotonic regression DLT estimates (0/3, 1/6, 1/6, 4/15, 2/4) = (0%, 16.7%, 16.7%, 26.7%, 50%), which monotonically increases with the dose level. Based on this isotonic estimate, assuming that the trial goal is to find the dose with the DLT rate of 30%, Dose Level 4 will be selected as the MTD. If there are no violators of the dose-toxicity monotonicity assumption, isotonic regression directly uses the observed DLT rates as the final estimates for MTD selection. For subjects who undergo intra-subject dose escalation, only DLTs that occur during the DLT period on the subject's initial dose level the assignment will be used for MTD determination.

In the case of dose levels with estimated toxicity of equal distance (tied dose levels) from the target toxicity of 30%, the following approach will be used: among all tied dose levels the highest dose level with target toxicity \leq 30% will be selected, unless all tied dose levels have estimated toxicity \geq 30%, in which case the lowest dose level will be selected.

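### The MTD selection rule does not exclude doses closed as unacceptably toxic, so in two uncommon patterns it names a closed dose as the MTD

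*Protocol*

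**What the plan says.** Protocol 9.1 and SAP 3.2 close a dose, and every dose above it, once the posterior probability that its DLT rate exceeds 30% reaches 95%. Table 7 (SAP Table 2) marks these cells DU and says the dose is not used again. Protocol Appendix 16.1 applies the same closure when the first two subjects both have a DLT.

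The final MTD is chosen by a separate rule. Protocol 9.2.4: "the MTD is the dose for which the isotonic estimate of the DLT rate is closest to the target DLT rate of 30" per cent. SAP 8.1 fits the same isotonic regression and says "The target DLT rate is then used to select the MTD"; its worked example and tie rule imply the same nearest-to-30% choice.

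On when an MTD is due, protocol 9.2.4 says "A MAD will be reported if the observed DLT rate is <25% among all dose levels. Otherwise, an MTD will be reported". SAP 8.1 agrees: "Otherwise, an MTD will be reported. Isotonic regression is a way to estimate the MTD under the assumption that toxicity increases with dose". Neither section mentions the DU bar or an outcome in which no MTD is identified.

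On schedules, SAP 3.1 says the "MTD or MAD may be determined for either Schedule 1 or Schedule 2". Protocol 3.3 says "The starting dose on Schedule 2 will be at a dose level that has completed evaluation for safety on Schedule 1". Protocol 3.1 says "the Sponsor may also elect to stop enrollment in Schedule 2 early (e.g., based on safety) and resume enrollment in Schedule 1".

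**The concern.** The escalation rule and the estimation rule are not connected. A dose closed because it is very probably above the target rate remains a candidate for the MTD. It wins if its estimate is nearer to 30% than any other, or if there is no other dose to choose. A programmer following protocol 9.2.4 literally would return it.

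Identifying the MTD or MAD is a primary objective, so the study could report as maximum tolerated a dose that its own safety rule had closed. The MTD is also named as the ceiling for the pharmacodynamic cohort (protocol 3.1) and for intrasubject escalation (protocol 3.3.1).

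**Working it through.** **Inputs.** Target rate 30%, Beta(1,1) prior, stay interval (0.25, 0.35), 95% bar, cohorts of about 3 and a maximum of 12 per dose (protocol 3.1, 9.1); nearest-to-30% isotonic rule (protocol 9.2.4, SAP 8.1).

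**Reproducing Table 7.** The pure mTPI-2 calculation matches 73 of the 75 filled cells. The other two (3/12 = E, 4/12 = D) follow the plan's explicit 12-subject rule. Every DU cell matches.

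**Distances.** With x DLTs in n, the bar applies when the Beta(1+x, 1+n−x) tail above 0.30 is at least 0.95. Distance is |x/n − 0.30|; a 0% dose is at 0.300.

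| Result | Tail above 0.30 | Distance | Chosen over a 0% dose? |
|---|---|---|---|
| 2/2 | 0.973 | 0.700 | no |
| 3/3 | 0.992 | 0.700 | no |
| 4/6 | 0.971 | 0.367 | no |
| 5/9 | 0.953 | 0.256 | yes |
| 6/10 | 0.978 | 0.300 | tie |
| 6/11 | 0.961 | 0.245 | yes |
| 7/12 | 0.982 | 0.283 | yes |

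With cohorts of exactly 3, only 5/9 and 7/12 matter. If cohorts of 4 occur (allowed in protocol 9.1), 6/10 ties a 0% dose: the protocol tie rule takes the higher, closed dose and the SAP tie rule takes the 0% dose.

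**First pattern: closed dose above clean doses.** Take 0/3, 0/6, 5/9 at levels 1 to 3. Level 3 is closed (Appendix 16.1, Step 3), yet it is nearer to 30% (0.256) than level 2 (0.300), so both documents name level 3. A 5/9 dose wins only if every lower estimate is below 0.300 − 0.256 = 4.4%; a 7/12 dose only if all are below 0.300 − 0.283 = 1.7%. One DLT in 12 at the dose below (8.3%, distance 0.217) removes the problem.

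The direct path 1/3, 2/6, 5/9 at a dose with true rate p has probability 3p(1−p)² × 3p(1−p)² × p³ = 9p⁵(1−p)⁴. That is 1.76% at p = 0.50, with a maximum of 1.86% at p = 0.556. Other routes need re-entry to the dose after a D.

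**Overall probability that a closed dose is named.** This is an exact enumeration with cohorts of 3 and weighted pooling of adjacent violators. The documents do not fix when escalation ends, so three conventions are assumed: (a) stop at 21 subjects; (b) run until a dose reaches 12; (c) no re-entry after a D, stopping at 6 subjects below a de-escalated or closed dose. Enrolment is assumed to continue after a D at the lowest dose.

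| Assumed true DLT rates (%) | (a) | (b) | (c) |
|---|---|---|---|
| 5, 10, 20, 30, 50 | 1.01% | 0.62% | 0.29% |
| Range over five graded curves* | 0.46–2.21% | 0.46–1.95% | 0.17–1.50% |
| Steep: 1, 2, 3, 5, 50 | 1.68% | 7.65% | 1.44% |
| Steep: 1, 2, 3, 50, 70 | 6.35% | 10.37% | 1.80% |

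*The first row plus (2,5,10,20,30), (5,15,30,45,60), (1,5,10,30,60) and (15,30,45,55,65).

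The larger figures come mainly from re-entry. On the last curve it contributes 4.46 of 6.35 points under (a) and 8.78 of 10.37 under (b), the latter being 7.38 at 5/9 and 1.40 at 7/12.

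**Second pattern: the only dose tried is closed.** Its observed rate exceeds 25%, so an MTD is required and there is one candidate; after 3/3 or 2/2 its estimate is 100%. Let r = 3p(1−p)². If a D ends enrolment, the probability of closure is p³(1 + r + r²), from 3/3, 4/6 and 5/9. A fourth cohort cannot close the dose, because 6/12 is D. If the two-in-two bar is always applied (an assumption), it is p² + p³(r + r²).

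- Schedule 2 starting dose, p = 0.20: r = 0.384; 0.008 × (1 + 0.384 + 0.147) = 1.2%. With the two-in-two bar: 0.04 + 0.384 × 0.008 + 0.384² × 0.008 = 4.4%.
- Schedule 2 starting dose, p = 0.30: r = 0.441; 0.027 × (1 + 0.441 + 0.194) = 4.4%. With the two-in-two bar: 10.7%.
- Level 1 on Schedule 1, p = 0.10: 0.13%, or 0.25% if enrolment continues after a D. With the two-in-two bar: 1.03% or 1.11%. At p = 0.05 with that bar: 0.25% or 0.26%.

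The Schedule 2 figures cover only closure before any other dose is tried on Schedule 2. The sponsor must also stop that schedule rather than de-escalate.

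**The case against.** The strongest reply is that this is a labelling matter. A closed dose stays closed, the RP2D rests on the totality of data (protocol 3.1.1, SAP 3.1), and the pharmacodynamic cohort and intrasubject escalation also require a dose that has completed its safety evaluation. SAP 8.1 tabulates DLT counts by schedule and level, so a 5/9 or 3/3 would be visible. All of this stands, and it limits the harm to a wrong reported MTD.

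The steep-curve figures depend on chosen curves and on re-entry after a D, which Appendix 16.1 does not work through. That also stands; without re-entry, no curve in the table exceeds 1.80%.

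The Schedule 2 case needs several discretionary steps, and an MTD only may be determined for a schedule, so it is possible rather than expected. On level 1, the SAP Table 1 notes on infusion duration at 3 and 10 mg/kg suggest that escalation had already passed it. That bears on conduct and does not make the written rule sound.

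The fix brings no clear gain in dose selection. On graded curves it lowers selection of doses with true rate above 40% by 0–0.50 points and correct selection by 0.03–0.87 points. Most too-toxic selections come from D doses, which it leaves alone. The case for it is consistency between two rules.

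The discretion in SAP 5.3.1, under which "the study team will review the data to assess which statistical analyses are still considered appropriate", does not close the gap. It applies only if the study itself is prematurely discontinued, names no no-MTD outcome, and by its wording does not reach the stopping of Schedule 2 alone. None of the four changes in SAP 11 concerns MTD selection.

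**Conclusion.** The concern holds. Followed as written, protocol 9.2.4 and SAP 8.1 can name as MTD a dose that protocol 9.1 and SAP 3.2 have closed, and they offer no alternative when a closed dose is the only one tried. This is an error in a stated rule for a primary-objective output. It is worth correcting but does not threaten the trial.

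The first pattern and the tail probabilities follow directly from the documents. The frequencies rest on the assumed DLT curves, the three assumed stopping conventions, cohorts of exactly 3 and weighted pooling: 0.17–2.21% on graded curves and 1.44–10.37% on steep ones. Confidence is high in the gap and lower in any single frequency.

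**What to change.** Add to SAP 8.1, list it in SAP 11, and align protocol 9.2.4 at the next amendment:

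> Within each schedule, isotonic regression is fitted to all tried doses. Any dose barred as unacceptably toxic on that schedule (DU in Table 2, or 2 DLTs in the first 2 subjects per protocol Appendix 16.1), and all doses above it, is not eligible for selection as the MTD for that schedule. If no eligible dose remains, it will be stated that no MTD was identified for that schedule.

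Also qualify the sentence requiring an MTD in all other cases so that it applies only if an eligible dose remains.

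Under this rule 0/3, 0/6, 5/9 gives level 2, and 3/3 at the only dose tried gives no MTD. Patterns that already resolve properly, such as 0/3, 1/6, 5/9 (level 2), do not change. It also removes the protocol–SAP conflict at 6/10 against a 0% dose.

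The cost is three sentences and one clause in SAP 8.1 and one line in SAP 11, with no new data. A dose closed by chance will occasionally be excluded, and the dose named instead may have a 0% estimate on few subjects. On the two steep curves, where the dose nearest to 30% itself has a true rate of 50%, its selection falls by 1.4–10.3 points. On (1, 2, 3, 50, 70%), selection of a dose with true rate above 40% falls from 54.4% to 48.2% under (a), 53.2% to 42.8% under (b), and 40.4% to 38.6% under (c).
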